### **3.3. Assessments during the study.**

The timing of events as per the schedule in Table 1 above is based on the date of receiving VST infusion (dose escalation phase) or from randomization (randomized phase). Additional follow up assessments may be done based on clinical and laboratory responses.

All assessments are considered standard-of-care unless identified.

#### Pre-treatment/Randomization.

1. Consenting
2. Patient HLA-typing to identify a suitably matched VST line
3. Confirmation of positive COVID test within 5 days of informed consenting
4. Pregnancy test\* if female patient of childbearing potential and (if a transplant recipient) has received a reduced intensity transplant regimen
5. Chest radiograph if not already done in the past 48 hours.

#### Day of Treatment/Randomization.

1. History and physical exam including height and weight
2. CBC with differential
3. Basic chemistry
4. Chemistries: liver function tests (bilirubin, alkaline phosphatase, AST, ALT), ferritin, DDimer, LDH and CRP
5. Blood and serum for ancillary lab studies
6. T cell infusion in the treatment arm of the randomized phase of the study should occur within 48 hours of assignment to treatment arm.
7. Acute GVHD and CRS/ICANS evaluation (only for treatment arm)

#### Post-Treatment/Randomization.

1. Daily Clinical improvement as measured by the ordinal scale (until day 14)
2. Daily history, collect blood and serum for ancillary lab studies, and CBC with differential (until day 14 or until discharge from hospital whichever comes first, refer to Table 1 for more details)
3. Chest-imaging (at least once post infusion by day 14)
4. Case Report Form (CRF) to include:
  - a. Complete acute GVHD staging and grading information (including skin, liver, upper and lower GI) assessed at a minimum weekly for the first 2 weeks and longer until resolution of GVHD if it develops (only for treatment arm).
  - b. Chemistries: liver function tests (bilirubin, alkaline phosphatase, AST, ALT), ferritin, DDimer, LDH and CRP, done at least weekly while hospitalized. If discharged no further chemistry testing is necessary.
  - c. Infusion-related toxicities assessed at a minimum weekly for the first 2 weeks and longer until resolution of any treatment related adverse events. (only treatment arm). This must include at least weekly assessment of immune effector related toxicities like CRS/ICANS per ASTCT grading.

#### Late follow-up visits (at months 2, 3 and 6), if outpatient:

1. History: in the BMT clinic on Walter Tower 15 (Houston Methodist Hospital). Can alternatively be done via teleconference
2. Laboratory studies: Optional for these visits. If collected then will be performed at the BMT clinic on Walter 15 (Houston Methodist Hospital).

3. Findings which are deemed to be treatment related at these late follow-up visits will be managed by infectious diseases and cell therapy trained attendings (Principal and co-investigators on study) at Houston Methodist Hospital.

There are no plans for compensation for injuries related to this study.

### **3.4. Modified Follow-Up, Off-study & Stopping rules.**

#### **3.4.1. Criteria for placing study on hold.**

**3.4.1.1.** Any patient who develops Grade  $\geq 3$  acute GVHD or Grade  $\geq 3$  treatment-related (at least possibly related) adverse event, excluding CRS or ICANS, post VST infusion. In such patients, the toxicities will be followed until resolution or until their off study date but no new patients will be treated until reviewed by the data safety board and reported to the FDA. For the purposes of the dose escalation phase of this study this would qualify as a DLT.

**3.4.1.2.** Any patient who experiences grade  $\geq 3$  CRS or ICANS that persists beyond 72 hours and worsens despite 2 doses of tocilizumab/Anakinra treatment irrespective of attribution to VSTs. In such patients, the toxicity will be followed until resolution or until their off study date. For the purposes of the dose escalation phase of this study this would qualify as a DLT.

**3.4.1.3.** Any patient who experiences grade II acute GVHD that persists  $>14$  days from onset or which is refractory to systemic steroid treatment (defined as no improvement in overall grade within 7 days of initiation of systemic steroids at 2 mg/kg/day). For the purposes of the dose escalation phase of this study this would qualify as a DLT.

**3.4.1.4.** If the first 2 patients treated at any DL or any 2 consecutively treated patients that receive VSTs during the randomized phase experience grade  $\geq$  II CRS or ICANS that persists for 7 days or is non-responsive to 2 doses of tocilizumab/Anakinra irrespective of attribution. For the purposes of the dose escalation phase of this study this would exceed the DLT boundary and would then study 3 additional patients at a lower dose level or if this were to occur on DL1 would stop accrual until a review is conducted.

Patients who meet these criteria will remain on follow-up as per the required assessments [Table 1](#).

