### **2.6.3. Informed Consent and Randomization.**

The informed consent process will begin at recognition of a subject who meets all eligibility criteria and consents to participation after a discussion with the study team (informed consent process). Consent may be obtained by teleconference. Once enrolled, blood will be taken from the subject for baseline immune response assessment and HLA-typing and if a partially HLA-matched VST line is available the subject will either receive treatment (dose escalation phase) or will be randomized (Randomized trial phase) to receive the partially matched VST line (in the treatment arm) or standard of care (in the control arm). If no VST line is identified, the patient will not proceed to treatment or randomization and will be removed from the study, but statistics on the proportion of patients who sign consent but are not treated or randomized will be reported.

Applicable only to the randomized phase, once randomized to the treatment arm, the patient must be infused with VSTs within 48 hours of randomization.

All consented patients will be registered in the online collaborative research environment (Forte's OnCore® eResearch CTMS), a Clinical Research Management System available at BCM Dan L. Duncan Comprehensive Cancer Center.

Enrollment to the dose escalation phase will be staggered. The first patient enrolled on each of the 3 dose levels (DL1, DL2 and DL3) will have to complete the 14-day toxicity monitoring window prior to enrollment of the next patients. Prior to dose escalation, all patients at a particular dose level should have completed the minimum 14-day toxicity monitoring window before enrolling to a higher dose level.

After the dose finding phase, patients will be randomized in a 1:1 ratio to receive SARS-CoVSTs at the MTD level or standard of care. Randomization will be performed in OnCore and use the permuted block method with a block size of 4 (2 in the treatment arm and 2 in the control arm). The purpose for a permuted block method is to ensure fairly random assignment during specific periods of surge with COVID19.

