#### **2.6.5. Administration and Monitoring.**

Partially HLA-matched VSTs will be thawed and given by intravenous injection (in a syringe or a bag). Patients will receive partially HLA-matched VSTs as a single infusion. In the rare case where insufficient banked cell product is available, a lower number of cells may be infused with agreement of the principal investigator, patient and/or guardian and the treatment team.

**2.6.5.1. Premedications.** Patients without prior history of reaction to blood products generally do not require premedication. If patients receive premedication, Benadryl iv/po and/or Tylenol po/iv may be given at doses appropriate for recipient size.

**2.6.5.2. Monitoring immediately post-infusion.** Patients will be monitored according to institutional standards for administration of blood products and at a minimum will be monitored according to below:

- Patients should remain on continuous pulse oximetry for at least 30 minutes
- Vital signs should be monitored at the end of infusion then at 30 and 60 minutes

**2.6.5.3. Supportive Care.** Patients will receive supportive care for acute or chronic toxicity, including infusion reaction, antibiotics and as indicated antipyretics for fevers, and other interventions as appropriate.

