### **3. PATIENT EVALUATION**

#### **3.1. Safety**

Patients will be closely monitored for a minimum of 14 days for toxicities or until all treatment related toxicities have resolved. Except as noted below (in section 3.4.1), the safety endpoint [dose limiting toxicities (DLT) for the dose escalation phase or treatment-related adverse event (tAE) for the randomized phase] will be defined as any acute GvHD (grade  $\geq 3$ ), grade  $\geq 3$  CRS or ICANS, grade  $\geq 3$  hematologic toxicity or grade  $\geq 3$  non-hematologic adverse events related to the T cell product within 14 days of the VST infusion and that are not due to pre-existing conditions as defined by the NCI Common Terminology Criteria for Adverse Events (CTCAE), Version 5.

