### 4.2 Dose Finding Phase

Three dose levels will be evaluated (Section 2.5). Dose escalation will be guided by the standard 3+3 design in order to determine the maximum tolerated dose (MTD) of SARS-CoVSTs. Detailed definitions of DLT are described in Section 3.1 and Section 3.4.1. The specific procedure is as follows: Starting from dose level 1 and escalating to the highest level sequentially, a cohort of three patients will be enrolled at each dose level, with a stagger to wait until the first patient on each dose level completes the 14-day toxicity monitoring window prior to enrollment of the other two patients. Dose level to the subsequent new cohort will not be assigned until the patients in the previous cohort have finished their 14-day period and their toxicity evaluations have become available. If no DLT is observed in any of the first 3 patients, the dose level will be escalated to the next dose level. If DLT is observed in 1 of the 3 patients, 3 more patients will be enrolled at the same dose level. If DLT is observed in no more than 1 out of 6 patients then we will advance to the next dose level. If DLT is observed in 2 or more patients at a same dose level then the MTD has been exceeded and the next lower dose level will be considered as the MTD level, if 6 patients have already been treated at that level. If only 3 patients have been studied at the MTD, 3 more patients will be enrolled at the MTD level to confirm that no more than 1 out of 6 patients have a DLT. Escalation will not proceed past dose level 3. If none of the dose levels has more than one patient who develops a DLT, then the highest dose level will be defined as the MTD. Patients who develop DLTs or complete 14-day monitoring periods after the VST infusion are considered DLT evaluable. Any patients who drops off the study early before day 14 due to a non-DLT-related reason will be replaced.

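### One limb of a listed DLT cannot occur within the 14 days used to count DLTs, and the protocol does not settle which CRS/ICANS wording defines a DLT or a tAE

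*Protocol*

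**What the plan says.** **Which events are DLTs.** Section 4.2 states: "Detailed definitions of DLT are described in Section 3.1 and Section 3.4.1". Section 2.1.1, the primary endpoint of the dose-finding phase, cites 3.1 only and sets day 14 after infusion as the cut-off. Section 3.1 lists grade 3 or higher events related to the product, "within 14 days of the VST infusion and that are not due to pre-existing conditions", but opens by excepting what 3.4.1 says.

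**The GVHD criterion.** Section 3.4.1.3 concerns grade II acute GVHD with two alternatives: persistence for more than 14 "days from onset or which is refractory to systemic steroid treatment", the latter judged 7 days after systemic steroids begin. It adds: "For the purposes of the dose escalation phase of this study this would qualify as a DLT".

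**The CRS/ICANS criterion.** Section 3.1 includes grade 3 or higher CRS or ICANS without a duration condition. Section 3.4.1.2 includes it where it is of a kind "that persists beyond 72 hours and worsens despite 2 doses of tocilizumab/Anakinra treatment irrespective of attribution to VSTs", and also labels it a DLT for dose escalation.

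**When a patient counts.** Section 4.2: "Patients who develop DLTs or complete 14-day monitoring periods after the VST infusion are considered DLT evaluable". Section 2.6.3 requires that "all patients at a particular dose level should have completed the minimum 14-day toxicity monitoring window before enrolling to a higher dose level". The only replacement rule in 4.2 is for patients who leave before day 14 for a reason other than a DLT.

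**Cell number.** Section 2.6.5: "In the rare case where insufficient banked cell product is available, a lower number of cells may be infused". No minimum is given, and 4.2 sets no dose-received condition.

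**The tAE.** Section 4.3 takes the tAE for the stopping boundary from 3.1. Section 4.6 reports DLT/tAE incidence as defined in 3.1 and 3.4.1.

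**The concern.** A 3+3 design decides on very few patients, so it needs to be clear on the decision day whether each patient has had a DLT. Here a patient can complete 14 days, be evaluable and have no DLT on record while carrying an event that becomes a listed DLT some days later. The next level, or the randomized phase at the dose called the MTD, can open on an incomplete count, and the protocol does not say how to recount afterwards.

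The CRS/ICANS wording raises a different problem. Two sections define the same toxicity differently, and other sections cite one or both. Section 2.8.2 anticipates CRS in these patients, so the case is not remote. The choice of wording affects the DLT count, and it may also make the events that feed the stopping boundary in 4.3 differ from those in the rate reported under 4.6.

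**Working it through.** **1. The plan's own counts.** The maximum is 3 levels × 6 = 18. With no DLTs the path is 3 + 3 + 6 (three more at the top level to confirm the MTD) = 12. Both match 4.5, so I am reading the escalation rule as the protocol intends.

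**2. Day arithmetic for 3.4.1.3.** In whole days from infusion, the persistence limb is first met on onset day + 15; the steroid limb is judged on start day + 7.

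| GVHD onset | Persistence limb first met | Steroid start | Steroid limb judged |
|---|---|---|---|
| day 0 | day 15 | day 0 | day 7 |
| day 7 | day 22 | day 7 | day 14 |
| day 14 | day 29 | day 8 | day 15 |

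Onset cannot precede infusion, so more than 14 days from onset is always more than 14 days from infusion. The persistence limb never fits the window. The steroid limb fits if steroids start by day 7.

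**3. Who is affected, given the stagger.** The first patient at a level completes 14 days before the other two enrol, and those two then complete 14 days. The first patient therefore has at least 14 + 14 = 28 days of follow-up when the next level opens, enough to see the persistence limb for onset up to day 13 (13 + 15 = 28). If a level is expanded, its first three patients likewise have at least 28 days. The patients with only the minimum 14 days are the last enrolled: the second and third of a three-patient cohort, or the added three of an expanded one.

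**4. What one reclassified patient does.** Under 4.2, a true 2/6 seen as 1/6 turns a level that exceeds the MTD into one that is passed. A true 1/3 seen as 0/3 skips three further patients. A true 1/6 seen as 0/6 changes nothing.

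**5. CRS/ICANS, side by side.** I read the relatedness phrase at the end of the 3.1 list as covering every item.

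| Grade 3 or higher CRS/ICANS | 3.1 | 3.4.1.2 |
|---|---|---|
| Related, resolves within 72 hours | counts | does not count |
| Unrelated, persists beyond 72 hours and worsens after two doses | does not count | counts |

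If the relatedness phrase covers only the last item of the list, the second row no longer differs but the first still does.

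**6. Illustrative probabilities.** With DLT rate p, P(level passed) = P(0/3) + P(1/3) × P(0/3) = (1−p)³ + 3p(1−p)⁵.

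- p = 0.05: 0.857 + 0.116 = 0.973
- p = 0.20: 0.512 + 0.197 = 0.709
- p = 0.25: 0.422 + 0.178 = 0.600
- p = 0.30: 0.343 + 0.151 = 0.494

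For the GVHD gap, assume a true DLT rate of 30% and vary the share of DLTs not yet classified at the decision. P(level passed) is 49.4% if none are missed, 55.7% at 10% missed, 65.4% at 25% (p = 0.30 × 0.75 = 0.225) and 81.4% at 50%. These shares apply to all patients at the level, so given step 3 they overstate the effect for a given rate of late events.

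For a reduced cell number, assume one of the first three patients carries half the DLT rate (15% instead of 30%): 49.4% becomes 56.4%.

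Every rate in this step is an assumption.

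**The case against.** The other side has good material.

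- **Follow-up does not stop at day 14.** Section 2.6.3 calls 14 days a minimum, 3.1 monitors until treatment-related toxicities resolve, the post-treatment list in 3.3 continues GVHD grading to resolution, and 4.2 waits for toxicity evaluations to become available. This stands as to observation. None of it delays the DLT count, escalation or the MTD declaration for a patient with unresolved grade II GVHD.
- **3.1 yields to 3.4.1.** So 3.4.1.3 may carry its own timing, and a late event is still a DLT and a ground for a hold. This stands. A reader might infer that such events are lost; they are not. The error is a decision taken too early.
- **The stagger narrows the gap, and significant GVHD is expected to be rare (2.8.1).** Both stand, and both limit the size.
- **Precedence can be read into the CRS/ICANS text.** 3.4.1.1 excludes CRS/ICANS and 3.4.1.2 then sets its own criterion, so for escalation 3.4.1.2 arguably governs. That is a reasonable reading, but 4.2 sends the reader to both sections and 2.1.1 to 3.1 alone. For the tAE, the DLT sentences in 3.4.1 are confined to dose escalation, yet 4.6 still cites 3.4.1.
- **Under-dosing is described as rare, and no sentence credits such a patient to the full level.** Correct. A reader might infer a stated rule from the silence of 4.2; the text supports only that the patient meets the evaluability definition and is not listed for replacement.

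**Conclusion.** The point holds in a limited form. It is certain by day arithmetic that the persistence limb of 3.4.1.3 cannot be met within the 14 days used by 2.1.1 and 4.2. It does not follow that the whole criterion is unobservable, since the steroid limb can fit. Nor is every patient exposed: the gap lies mainly with the last-enrolled patients of a cohort. For them, 4.2 as written allows escalation or an MTD declaration before a possible DLT has been classified.

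The CRS/ICANS conflict is separate and also holds. Sections 3.1 and 3.4.1.2 classify some events differently, and the cross-references in 2.1.1, 4.2, 4.3 and 4.6 do not settle which governs, so the boundary and the reported tAE rate may count different events.

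The reduced-cell-number point is minor and rests on silence.

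The size is not known. A reader might take the difference between 97% (5% DLT rate) and 60% (25%) as the expected effect of the CRS/ICANS wording. That would require brief related grade 3 CRS in 20% of patients, which nothing in the document supports; 1.5 and 1.6 report little or no CRS in earlier VST trials, though not in COVID-19 patients. The probabilities show only how sensitive the design is to classification. The case for correction is that DLT is the primary endpoint of this phase and sets the dose given to the 20 patients of the treatment arm.

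**What to change.** 1. Reconcile 2.1.1, 3.1, 3.4.1, 4.2, 4.3 and 4.6 into one DLT definition and one tAE definition, each stated once and cited elsewhere. State which CRS/ICANS wording applies to each. The clinical thresholds are for the investigators to choose.
2. In 4.2, state that a patient with an unresolved event that could still become a listed DLT is not counted as DLT-free, for escalation or for the MTD, until the event is classified. Alternatively, align the definitions and the window so that every listed DLT can be observed within it.
3. As a minor addition to 4.2, state that a patient who received fewer cells than assigned under 2.6.5 and had no DLT is not evaluable at that level and is replaced.

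The cost is protocol wording, an occasional wait past day 14, and at times one replaced patient. The maximum of 18 is stated in DLT-evaluable patients, so a replacement does not change it.

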## Appendix I

### Appendix I CRS Grading Scale per ASTCT guidelines

Grade	Symptoms
1	
 
• Symptoms are not life threatening and require symptomatic treatment only (e.g. fever, nausea, fatigue, headache, myalgia, malaise)
 

2	
 
• Symptoms require and respond to moderate intervention
 
• Oxygen requirement <40% or hypotension responsive to fluids or
 
• low dose of one vasopressor or Grade 2 organ toxicity
 

3	
 
• Symptoms require and respond to aggressive intervention
 
• Oxygen requirement ≥ 40% or hypotension requiring high dose or multiple vasopressors or
 
• Grade 3 organ toxicity or Grade 4 transaminitis
 

4	
 
• Life-threatening symptoms
 
• Requirements for ventilator support or Grade 4 organ toxicity (excluding transaminitis)
 

5	
 
• Death
 

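### In dose finding, two persistent or refractory grade II CRS/ICANS events stop escalation only if they fall in the first two patients at a dose level; in patients 1+3 or 2+3 the dose goes up

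*Protocol*

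**What the plan says.** **The trigger.** Protocol 3.4.1.4 opens: "If the first 2 patients treated at any DL or any 2 consecutively treated patients that receive VSTs during the randomized phase experience grade" II or higher CRS or ICANS that lasts 7 days or does not respond to two doses of tocilizumab/Anakinra, irrespective of attribution. It then states: "For the purposes of the dose escalation phase of this study this would exceed the DLT boundary". The consequence is three further patients at a lower level or, on DL1, an accrual stop pending review.

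**Other DLT definitions.** Section 4.2 takes its DLT definitions from 3.1 and 3.4.1.
- 3.1 requires grade 3 or higher for CRS/ICANS, related to the product.
- 3.4.1.1 leaves CRS and ICANS out.
- 3.4.1.2 requires grade 3 or higher CRS/ICANS that continues past 72 hours and worsens despite two doses.
- 3.4.1.3 concerns GVHD only.

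**Escalation.** Section 4.2 says: "If no DLT is observed in any of the first 3 patients, the dose level will be escalated to the next dose level". It also says: "If DLT is observed in 2 or more patients at a same dose level then the MTD has been exceeded", with no condition on which patients they are.

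**Stagger.** Under 2.6.3 the first patient at each level "will have to complete the 14-day toxicity monitoring window prior to enrollment of the next patients". Section 4.2 agrees: the wait is until "the first patient on each dose level completes the 14-day toxicity monitoring window prior to enrollment of the other two patients". Section 2.6.3 also requires every patient at a level to complete the 14 days before the next level opens.

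**The concern.** The protocol has decided that two patients with this event at one dose level are too many, but applies that decision only when the two are treated first. The same two events in patients 1+3 or 2+3 meet no DLT definition, so the cohort reads as 0 of 3.

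Patients 2 and 3 both become eligible to enrol once patient 1 has cleared the window, so which of them is infused second says nothing about the dose. Nor does the rule work only as an early look: the escalation decision waits for all three outcomes and then ignores the third.

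What is at stake is the dose decision. The levels in section 2.5 double at each step (1, 2 and 4 × 10^7 cells). On a missed pair:
- at DL1, the dose doubles instead of accrual stopping for review;
- at DL2, it doubles instead of stepping down;
- at DL3, there is no step down.

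**Working it through.** **The plan's figures.** The protocol gives no operating characteristic for 3.4.1.4, so there is none to reproduce. The section 4.5 sample sizes confirm the path being modelled: maximum 3 levels × 6 = 18, expected 3 + 3 + 6 = 12.

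**Patterns in one cohort.** Suppose the only toxicity is grade II CRS/ICANS meeting the 3.4.1.4 duration or response condition.

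| Patients affected | Result as written |
|---|---|
| none, or any one | 0 of 3 DLTs, escalate |
| 1+2 | boundary exceeded |
| 1+3 | 0 of 3 DLTs, escalate |
| 2+3 | 0 of 3 DLTs, escalate |
| 1+2+3 | boundary exceeded |

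Of the three possible pairs, one fires. This result needs no event rate.

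**Size.** The per-patient rate p is not in the protocol. I assume p = 0.05, 0.1, 0.2 and 0.3, with independent patients, equal p and no other DLTs.

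- Fires as written, per first cohort: p².
- Any 2 of 3: q = 3p² − 2p³.
- Missed pair: m = 2p²(1 − p) = q − p².
- At least one missed pair over up to three levels, counting only until the existing rule fires: m(1 + s + s²), where s = 1 − p² − m is the chance that a level has neither a firing nor a miss.

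Example at p = 0.2: p² = 0.04; q = 0.12 − 0.016 = 0.104; m = 0.064; s = 0.896; 0.064 × (1 + 0.896 + 0.8028) = 0.173.

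| | p = 0.05 | 0.1 | 0.2 | 0.3 |
|---|---|---|---|---|
| Fires as written, p² | 0.25% | 1.0% | 4.0% | 9.0% |
| Any 2 of 3, q | 0.7% | 2.8% | 10.4% | 21.6% |
| Missed per cohort, m | 0.48% | 1.8% | 6.4% | 12.6% |
| At least one miss, up to 3 levels | 1.4% | 5.3% | 17.3% | 30.2% |

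**Randomized-phase backstop.** For a run of two among 20 treated patients, let a(n) be the chance of no such run in n patients: a(n) = (1 − p)a(n−1) + p(1 − p)a(n−2), with a(0) = a(1) = 1. Then 1 − a(20) is about 4.4%, 16.1%, 48.8% and 76.8%.

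**The case against.** **It may be deliberate.** Section 2.8.2 expects CRS in COVID-19 patients, and in Appendix I an oxygen requirement below 40% is already grade 2. A patient who enters on room air and then needs nasal oxygen for a week could meet the criterion from COVID-19 alone. Requiring both of the first two patients keeps such background events from stopping the trial. This is a fair reason for keeping a single grade II event out of the DLT count, and it stands. It does not explain why the pair 1+2 should count and 2+3 should not. A 2+3 pair is consecutive and would hold the randomized phase, yet it passes in dose finding.

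**The effect may be small.** All the percentages rest on an assumed p. Section 4.5 expects no VST-related adverse events, and at p = 0.05 the miss is 0.48% per cohort. The larger rates are plausible only if COVID-caused events count, in which case many missed pairs would be background disease. This stands and holds the severity down.

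**There are backstops.** Grade 3 or higher CRS/ICANS can be a DLT, subject to relatedness under 3.1 or to persistence and worsening under 3.4.1.2. Before the MTD is confirmed, "If only 3 patients have been studied at the MTD, 3 more patients will be enrolled at the MTD level". The randomized phase has its own hold. These limit harm, but the expansion counts only DLTs, and patients 4 to 6 can never be the first two. No written rule covers a 1+3 or 2+3 pair.

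**Refractory events may be regraded.** Appendix I describes grade 2 as "Symptoms require and respond to moderate intervention", so a non-responding event might become grade 3. The gap is therefore mainly the 7-day condition, although 3.4.1.4 itself provides for non-responsive grade II.

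**Stronger readings the text does not support.** A reader might infer that 3.4.1.4 contradicts 4.2. It does not: these events are not DLTs, so 4.2 can be followed as written. A reader might also infer, by analogy with grade II GVHD in 3.4.1.3, that each such event should be a DLT. The protocol asks for two affected patients for CRS/ICANS, and its background-disease rationale is reasonable.

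**Conclusion.** The point holds as a badly chosen trigger in a safety rule. As written, the dose decision after two persistent or refractory grade II CRS/ICANS events in a three-patient cohort depends on treatment order, and two of the three possible pairs lead to escalation. That follows from the text alone.

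The probabilities rest on assumed rates and independence: from about 1.4% at p = 0.05 to 30.2% at p = 0.3 for at least one missed pair in the phase. At the low rates the sponsor's expectation implies, the absolute risk is small. Severity is low, and no sample size or power figure changes.

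**What to change.** In 3.4.1.4, change the dose-finding condition to *any 2 of the first 3 patients treated at any DL*. Add to 4.2 that meeting this criterion means the MTD is exceeded. The grade, duration, response and attribution terms stay, and a single grade II event remains a non-DLT.

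**Cost.** This is a wording amendment to two sections, with no added assessments. The rule fires more often, partly from COVID-19 itself: per first cohort 0.25% to 0.7%, 1% to 2.8%, 4% to 10.4% and 9% to 21.6% at the four assumed rates. Over up to three levels, 1 − (1 − p²)³ becomes 1 − (1 − q)³: 0.7% to 2.2%, 3.0% to 8.2%, 11.5% to 28.1% and 24.6% to 51.8%. Every added stop is a cohort with the same two events that the protocol already treats as too many.

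**Limit and option.** At a level with six patients there are 15 possible pairs. The present rule covers 1 and the revised wording covers 3. Only any 2 of up to 6 patients removes order dependence there. It would fire at a six-patient level with probability 1 − (1 − p)⁶ − 6p(1 − p)⁵ = 3.3%, 11.4%, 34.5% and 58.0%. Whether that is worth the extra stops is the sponsor's choice.

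### Sections 3.4.1.4 and 4.2 give different next steps when a dose level is exceeded and the next lower level already has 6 patients, which could change the MTD

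*Protocol*

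**What the plan says.** Protocol Section 3.4.1.4 covers the case where the first 2 patients at a dose level have grade II or worse CRS or ICANS that lasts 7 days or does not respond to two doses of the named agents, whatever the cause. It gives the consequence as "For the purposes of the dose escalation phase of this study this would exceed the DLT boundary". At DL2 or DL3 the trial "would then study 3 additional patients at a lower dose level". For DL1 it says "if this were to occur on DL1 would stop accrual until a review is conducted". It sets no condition on how many patients the lower level already has, and it does not say which lower level is meant.

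Section 4.2 gives the 3+3 procedure. Its rule for exceeding a level is "If DLT is observed in 2 or more patients at a same dose level then the MTD has been exceeded". Two branches follow:

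- 6 patients already at the level below: "the next lower dose level will be considered as the MTD level, if 6 patients have already been treated at that level".
- 3 patients there: "3 more patients will be enrolled at the MTD level to confirm that no more than 1 out of 6 patients have a DLT".

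Section 4.2 refers to Sections 3.1 and 3.4.1 for its DLT definitions. Neither 3.4.1 nor 4.2 says which governs if their actions differ.

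**The concern.** Sections 3.4.1.1 to 3.4.1.3 only classify an event as a DLT and leave dose assignment to 4.2. Section 3.4.1.4 adds a dose-assignment step of its own, and that step lacks the condition on numbers already treated that 4.2 applies.

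The state in which they differ is an ordinary 3+3 outcome. Section 4.2 escalates after 1 DLT in 6, so any expanded and cleared level has 6 patients when the next level opens. If the 3.4.1.4 event then occurs, the team has two written instructions.

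At stake are whether 3 more patients are infused and, possibly, which dose becomes the MTD. The MTD is the target of the dose-finding phase and sets the dose for the 20 patients in the randomized treatment arm.

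**Working it through.** **1. The plan's own sizes (Section 4.5).** Maximum: 3 levels × 6 = 18. Expected with no DLT: 3 + 3 + 6 = 12. Both figures reproduce.

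**2. The two sections side by side,** reading the lower level in 3.4.1.4 as the next lower one:

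| Next lower level at the trigger | Section 4.2 | Section 3.4.1.4 |
|---|---|---|
| 3 treated, 0 DLT | add 3, total 6 | add 3, total 6 |
| 6 treated, 1 DLT | add 0, level is the MTD | add 3, total 9 |

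In the second row, no DLT among the 3 added patients leaves 1 DLT in 9 and the MTD unchanged. One or more gives at least 2 DLTs at that level, which 4.2 treats as exceeded. The MTD then moves down, or no level qualifies if that level is DL1. The confirmation rule in 4.2 is written for 6 patients, not 9.

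**3. Does the cap of 18 exclude the extra cohort?** No. With DL1 and DL2 both expanded and 2 or 3 patients at DL3, the total after adding 3 is 6 + 6 + 2 + 3 = 17 or 6 + 6 + 3 + 3 = 18.

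**4. How often the next lower level has 6 patients.** The protocol gives no DLT rate by dose level, so the true rate p at the lower level is assumed.

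- Cleared with 6 patients: a = 3p(1−p)^5
- Cleared with 3 patients: b = (1−p)^3
- Share with 6, given escalation: a/(a+b)
- At least 1 DLT in 3 further patients: r = 1−(1−p)^3

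| p | a | b | a/(a+b) | r |
|---|---|---|---|---|
| 5% | 0.1161 | 0.8574 | 11.9% | 14.3% |
| 10% | 0.1771 | 0.7290 | 19.5% | 27.1% |
| 1/6 | 0.2009 | 0.5787 | 25.8% | 42.1% |
| 25% | 0.1780 | 0.4219 | 29.7% | 57.8% |

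If the trigger does not depend on how many were treated below, the sections agree in 1 − 0.297 = 70% to 1 − 0.119 = 88% of triggers.

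**5. How often it matters, per escalation step.** Let q be the assumed chance that a patient has the 3.4.1.4 event, independently between patients. The conflict arises with probability a·q² (lower level cleared with 6, then both first patients at the next level affected). The MTD changes with probability a·q²·r.

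| p | q = 5%: conflict / changed MTD | q = 20% | q = 50% |
|---|---|---|---|
| 5% | 0.03% / 0.004% | 0.46% / 0.07% | 2.9% / 0.41% |
| 10% | 0.04% / 0.012% | 0.71% / 0.19% | 4.4% / 1.2% |
| 1/6 | 0.05% / 0.021% | 0.80% / 0.34% | 5.0% / 2.1% |
| 25% | 0.04% / 0.026% | 0.71% / 0.41% | 4.4% / 2.6% |

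**6. Which lower level.** After a DL2 trigger only DL1 is lower. After a DL3 trigger, 3.4.1.4 can mean DL2 or DL1, whereas 4.2 means DL2. If DL1 were meant, the sections would differ even with 3 patients at DL2. These figures do not include that reading.

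**The case against.** The strongest reply is that 3.4.1.4 simply declares the boundary exceeded and then summarises the 3-patient branch of 4.2. On the path the protocol expects, with no DLT at the lower levels, the two sections do agree. Section 4.2 presents itself as the procedure and takes only definitions from 3.4.1. This reading is natural, but the text does not state it, so it softens the conflict without removing it.

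Second, the event falls under criteria for placing the study on hold. Sections 3.4.2 and 4.4 require approval by the study team, IRB, DSMB and FDA before the study resumes, so an unnoticed divergence is unlikely. That stands as mitigation. The reviewing bodies would still have two instructions in front of them.

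Third, the trigger may be rare. Section 4.5 anticipates no VST-related adverse event at any dose level. Eligibility excludes CRS above grade 1 and requires adequate oxygen saturation on room air. The event must occur in both of the first 2 patients. Because it counts whatever its cause, its rate could exceed the VST-related rate, but nothing in the protocol supports a rate as high as 20%. This objection stands, which is why the 5% case is shown.

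A reader might infer that the same data yield two different MTDs. The documents do not support that. At the trigger, one section names an MTD and the other asks for 3 more patients; the results part only if those new patients bring a further DLT. A reader might also take 0.5% to 5% as the chance of a changed MTD. It is the chance that the two instructions differ.

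**Conclusion.** The conflict is real but narrow. If the first 2 patients at DL2 or DL3 meet 3.4.1.4 and the next lower level has 6 patients with 1 DLT, the same data lead to different next steps and possibly a different MTD. For a DL3 trigger, the target level is also unclear.

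If 20% to 50% of patients are assumed to have the 3.4.1.4 event, with lower-level DLT rates of 5% to 25%, the conflict arises in about 0.5% to 5% of escalation steps and the MTD changes in about 0.07% to 2.6%. At an assumed event rate of 5%, a changed MTD is below 0.03%. All of these rates are assumptions. The textual conflict does not depend on them, but its practical weight does. Severity is low: the case for changing the text is that two stated dose-assignment rules disagree and reconciling them is cheap.

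**What to change.** Reconcile Sections 3.4.1.4 and 4.2 so that a single action follows the event. Both should state the same target level, the same condition on the number already treated there, and an acceptance rule for the number then treated. A cross-reference between the sections, saying which one governs, is one way to do this. The sponsor decides which version stands; this review does not favour either.

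The cost is about one sentence in the protocol. The edit itself needs no added visits or analyses.
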